1.1.2.1. Primary Objective

The primary objective of the study is to determine the efficacy of patisiran by evaluating the difference between the patisiran and placebo groups in the change from baseline of Modified Neuropathy Impairment Score (mNIS+7) score at 18 months.

1.1.2.2. Secondary Objectives

The secondary objectives of the study are to determine the effect of patisiran on various clinical parameters by assessing the difference between patisiran and placebo in the change from baseline in the following measurements at 18 months:

- Norfolk Quality of Life-Diabetic Neuropathy (Norfolk QOL-DN) Total QoL Score.
- Neuropathy Impairment Score-weakness (NIS-W) score.
- Modified body mass index (mBMI), calculated by multiplying the BMI (kg/m²) by serum albumin level (g/L).
- Timed 10-meter walk test speed (meter/second), calculated as 10 meters divided by the walking time (second).
- Autonomic symptoms questionnaire (Composite Autonomic Symptom Score [COMPASS-31]).

1.1.2.3. Exploratory Objectives

The exploratory objectives of the study are:

- To determine the difference between the patisiran and placebo groups in the change from baseline in the following measurements at 18 months:
 - NIS+7 score;

- Grip strength;
- EuroQOL (EQ-5D) questionnaire;
- Level of disability (Rasch-built Overall Disability Scale [R-ODS]);
- Large vs. small nerve fiber function including nerve conduction studies (NCS) 5 attributes ($\Sigma 5$), quantitative sensory testing by body surface area including touch pressure and heat pain (QST), vibration detection threshold (VDT), heart rate response to deep breathing (HRdb), postural blood pressure;
- Pathologic evaluation of sensory and autonomic innervation through voluntary skin punch biopsies and analysis of intraepidermal nerve fiber density (IENFD) and sweat gland nerve fiber density (SGNFD))
- Assessment of ambulation through FAP stage and Polyneuropathy Disability (PND) score;
- Cardiac assessment through echocardiogram, troponin I, and N-terminal prohormone of B-type natriuretic peptide (NT-proBNP) levels;
- Pharmacodynamic (PD) biomarkers (TTR, RBP, vitamin A);
- To compare the proportion of patients in the patisiran and placebo groups who meet the pre-defined criterion for rapid disease progression (defined as ≥ 24 -point increase in mNIS+7 from baseline [based on an average of 2 measurements] and FAP stage progression relative to baseline) at 9 months;
- To serially evaluate lower limb nerve injury via voluntary magnetic resonance (MR) neurography approximately every 6 months in a subset of patients receiving either patisiran or placebo who consent to perform this assessment.

1.2. Study Design

1.2.1. Synopsis of Study Design

This is a multicenter, multinational, randomized, double-blind study comparing patisiran to placebo in hATTR patients with symptomatic polyneuropathy.

Consented eligible patients will be randomized to receive either 0.3 mg/kg patisiran or placebo in a 2:1 ratio (patisiran to placebo) in a blinded manner. Randomization will be stratified by Neuropathy Impairment Score (NIS; < 50 vs. ≥ 50), early onset V30M (< 50 years of age at onset) vs. all other mutations (including late onset V30M), and previous tetramer stabilizer use (tafamidis or diflunisal) vs. no previous tetramer stabilizer use. Patients will receive patisiran or placebo once every 21 days for 78 weeks (18 months).

Patients will have efficacy assessments at Screening/Baseline, 9 months, and 18 months. Study personnel performing assessments related to the efficacy endpoints will be different from the Investigator and other personnel managing the patient, and all of these study personnel will be blinded to any clinical laboratory results that could potentially unblind them (e.g., TTR levels, vitamin A levels, thyroid function tests). In addition, the study personnel performing assessments related to the efficacy endpoints will also be blinded to the results of any previous assessments (e.g., Screening/Baseline, Baseline, or 9-month assessments). Whenever possible, the same site personnel (individual) will conduct efficacy assessments for a given patient across time points.

At the 9-month time point, if the clinical adjudication committee determines that a patient is exhibiting rapid disease progression (defined as ≥ 24 -point increase in mNIS+7 from baseline [based on an average of 2 measurements] and FAP stage progression relative to baseline), the patient's treating physician will provide the patient with the option of discontinuing study drug and receiving local standard of care treatment for FAP. Patients who discontinue study drug will remain on study, following a modified schedule of visits, through completion of the 18-month efficacy assessments and blinding will be maintained throughout.

Patients who complete the 18-month efficacy assessments can elect to participate in an extension study in which patients would receive open-label administration of 0.3 mg/kg patisiran once every 21 days.

A Data Monitoring Committee (DMC) will be implemented for the study and will operate under a pre-specified charter.

1.2.2. Randomization Methodology

Patients will be randomly assigned in a 2:1 ratio to receive either 0.3 mg/kg patisiran or placebo (normal saline 0.9%).

Patients will be randomized via an interactive response system (IRS). Either designated site personnel or the pharmacist may request randomization for the patient, but only the pharmacist or pre-identified unblinded personnel will be allowed to receive the randomized treatment code. The treatment code will be delivered to the unblinded personnel or the pharmacist to prepare the necessary number of vials for that patient based on their weight.

As described above in Section 1.2.1, the stratification factors for randomization include NIS (< 50 vs. ≥ 50), early onset V30M (< 50 years of age at onset) vs. all other mutations (including late onset V30M), and previous tetramer stabilizer use (tafamidis or diflunisal) vs. no previous tetramer stabilizer use.

1.2.3. Rapid Disease Progression

Patients who have evidence of rapid disease progression at 9 months (defined as ≥ 24 -point increase in mNIS+7 from baseline [based on an average of 2 measurements] and FAP stage progression relative to baseline) will be given the option of discontinuing study drug and receiving local standard of care treatment for their FAP. Those who elect this option will be asked to follow a modified study visit schedule and return for their 18-month efficacy assessment (blinding will be maintained throughout).

1.2.4. Withdrawals, Dropouts, Loss to Follow-up

Patients are free to discontinue treatment or withdraw from the study at any time and for any reason, without penalty to their continuing medical care.

There are 3 ways for a patient to discontinue treatment and/or withdraw from the study:

- 1) The patient or investigator decides to discontinue study treatment, but the patient agrees to remain in the study and undergo follow-up assessments;
- 2) The patient experiences protocol-defined rapid disease progression at Month 9 and elects to discontinue study treatment but remain in the study and return for protocol-specified visits, including follow-up assessment at Month 18;
- 3) The patient decides to no longer participate in the study and withdraws consent.

A patient will be considered to have completed the study if the patient does not withdraw consent from the study and completes protocol-specified procedures up through the 18-month efficacy assessment visit.

1.2.5. Unblinding

Unblinding is only to occur in the case of patient emergencies or when necessary from a regulatory reporting perspective (e.g., Suspected Unexpected Serious Adverse Reaction [SUSAR] occurring in the EU), and at the conclusion of the study.

Patients who discontinue study drug at 9 months due to rapid disease progression will remain blinded throughout the remainder of the study.

In the event that the Investigator requests to know a patient's study treatment assignment, the Investigator is instructed to contact the Contract Research Organization (CRO) Medical Monitor to discuss the need for unblinding. In case of an emergency, the treatment allocation for each patient will be available from the unblinded site personnel, pharmacist, or the IRS system.

If a patient becomes pregnant or seriously ill during the study, the blind should be broken only if knowledge of the treatment administered will affect treatment options available to the patient. Before breaking the blind, the Principal or Sub-investigator should attempt to contact the CRO Medical Monitor. If the Medical Monitor is immediately unreachable, the Principal or Sub-investigator should break the blind as necessary using the code breaking information provided and contact the CRO Medical Monitor as soon as possible. A record will be kept of when the blind was broken, who broke it, and why.

1.2.6. Study Procedures

The schedule of assessments is described in the study protocol (Table 1-1, Table 1-2, and Table 1-3).

1.2.7. Efficacy, Pharmacokinetic, Pharmacodynamic, and Safety Parameters

1.2.7.1. Efficacy Parameters

Efficacy parameters will include the following. All evaluations will be conducted at baseline and at 9 and 18 months (except for mBMI as described below).

Primary Endpoint

- Neurologic impairment will be assessed using the mNIS+7 composite score (range: 0 to 304 points). The mNIS+7 include the modified NIS (weakness and reflexes), Σ 5 NCS, QST, as well as autonomic assessment through postural blood pressure. Two assessments will be performed at each visit; each component contributing to the composite score is the average of the 2 assessments. A scoring algorithm, including methods for handling missing components of the mNIS+7, is included in Appendix 7.2.1.

Secondary Endpoints

- Patient reported QOL will be evaluated using the Norfolk QOL-DN total score (range: -4 to 136 points). A scoring algorithm for this instrument is included in Appendix 7.2.2.
- Motor strength will be evaluated using NIS-W, calculated as the average of the 2 assessments performed at each visit (range: 0 to 192 points).

- Level of disability will be assessed using the Rasch-built Overall Disability Scale (R-ODS; range: 0 to 48). A scoring algorithm for the R-ODS is included in Appendix [7.2.4](#).
- Functional status will additionally be assessed by 10-meter walk gait speed.
- Nutritional status will be assessed using mBMI, calculated by multiplying the BMI (kg/m²) by serum albumin level (g/L). mBMI will be assessed at baseline, Day 84, Day 189, Day 357, Day 462 and Day 546.
- Autonomic symptoms will be assessed using the COMPASS-31 total score (range: 0 to 100 points). A scoring algorithm for the COMPASS-31 total score and domain scores is included in Appendix [7.2.5](#).

Exploratory Endpoints

Exploratory endpoints are detailed in Section [1.1.2.3](#).

In addition, the evaluation of dermal amyloid content (% Congo Red staining) using same skin punch biopsy specimens analyzed for nerve fiber density (SGNFD and IENFD) will also be assessed as an exploratory endpoint.

1.2.7.2. Pharmacokinetic Parameters

Blood samples for determination of patisiran pharmacokinetics (PK) will be collected as outlined in the schedule of assessments. Plasma siRNA, DLin-MC3-DMA, and PEG₂₀₀₀-C-DMG concentrations will be determined in all patients in order to estimate individual PK parameters such as peak and trough concentrations.

Urine will be collected with void volume recorded for all patients at time points specified in the schedule of assessments to determine concentration of siRNA and 4-dimethylaminodibutyric acid (the metabolite of DLin-MC3-DMA) after dosing with study drug.

Pharmacokinetic parameters will be estimated by the Clinical Pharmacology and Pharmacometrics Department at Alnylam Pharmaceuticals.

1.2.7.3. Pharmacodynamic and Pharmacology Parameters

Pharmacodynamic markers assessed serially will include serum TTR, vitamin A, and RBP. Additional blood samples will be collected for exploratory biomarkers related to FAP. Anti-drug antibodies (ADA) data will also be collected.

1.2.7.4. Safety Parameters

Safety evaluations to be performed during the study include monitoring of adverse events (AEs) and concomitant medications, physical examinations, measurement of vital signs, 12-lead ECGs, clinical laboratory evaluations including hematology, clinical chemistry (including liver function tests), thyroid function parameters, urinalysis, and ophthalmology examinations.

Suicidal ideation and behavior will be assessed using the Columbia–Suicide Severity Rating Scale (C-SSRS) questionnaire.

2. PATIENT POPULATION

2.1. Population Definitions

The following patient populations will be evaluated and used for presentation and analysis of the data:

- Modified Intent-to-Treat (mITT) population: All patients who were randomized and received at least 1 dose of patisiran or placebo. Patients will be analyzed according to the treatment to which they were randomized.
- Per-protocol (PP) population: All randomized patients who received at least 1 dose of patisiran or placebo, completed baseline and either 9-month or 18-month mNIS+7 and Norfolk QOL assessments, and did not experience any major protocol deviations that may impact the efficacy results (Section 2.2). Patients will be analyzed according to treatment received.
- Safety population: All patients who received at least 1 dose of patisiran or placebo. Patients will be analyzed according to the treatment received.
- PK population: All patients in the Safety Population who provided at least 1 PK concentration measurement.

The primary population for efficacy analysis will be the mITT population; the primary endpoint and the first secondary endpoint (Norfolk QOL) will also be analyzed using the PP population. The remaining secondary and exploratory efficacy endpoints will be analyzed using the mITT population only. Safety analysis will be conducted in the safety population. PK analysis will be conducted in the PK population.

2.2. Protocol Deviations

A deviation is considered any departure from the procedures set forth in the protocol. Protocol deviations will be classified into major and minor by medical review and recorded prior to database lock. A major deviation is a deviation that may impact patient safety or efficacy interpretation (for example, failure to meet key inclusion and exclusion criteria). Deviations not designated as major will be considered minor.

The Sponsor or designee will be responsible for producing the final protocol deviation file (formatted as a Microsoft Excel file). This file will include a description of each protocol deviation and whether or not this deviation is classified as a major deviation. In addition, each major deviation will be clearly identified as to whether or not it warrants exclusion from the Per Protocol population, based on the potential impact on the efficacy results according to the judgment of the sponsor. This file will be finalized prior to database lock and unblinding of treatment assignments for all patients.

The following are some examples of key inclusion/exclusion criteria. Failure to meet such criteria may warrant the exclusion from the Per Protocol population:

Inclusion:

1. Have a diagnosis of FAP with documented TTR mutation;
2. Have an NIS of 5 to 130 (inclusive) and a PND score of $\leq 3b$;
3. Have a Karnofsky performance status of $\geq 60\%$.

Exclusion:

1. Had a prior liver transplant or is planning to undergo liver transplant during the study period;
2. Has known primary amyloidosis or leptomeningeal amyloidosis;
3. Has known type I diabetes;
4. Has had type II diabetes mellitus for ≥ 5 years;
5. Received an investigational agent or device within 30 days of anticipated study drug administration or 5 half-lives of the investigational drug, whichever is longer;
6. Participated in a clinical trial with antisense oligonucleotide, must have completed a 3-month wash-out prior to start of the study drug administration in this study.

All protocol deviations and major protocol deviations will be presented in data listings.

3. GENERAL STATISTICAL METHODS

3.1. Sample Size Justification

For the estimation of sample size, a mean (\pm SD) mNIS+7 progression rate (primary endpoint) in the placebo group of 24 ± 16 points over 18 months was estimated using natural history data [1] from FAP patients. A sample of 154 patients provides 90% power for a 2-sided t-test with an 8.95-point (37.5%) mean difference between treatment arms in the primary endpoint at 2-sided $\alpha = 0.05$. Assuming a 25% random premature discontinuation rate (due to liver transplantation or other factors), the required sample size for this study is approximately 200.

3.2. General Methods

All data listings that contain an evaluation date will contain a study day relative to the day of the first dose of study drug, which is designated as Day 1. On-treatment study days will be calculated as evaluation date – first dose date +1 and pre-treatment days will be calculated as evaluation date – first dose date. For example, the day prior to study drug administration will be Day -1, the first dose day of study drug will be Day 1 and the day after the first dose of study drug will be Day 2, etc.

All output will be incorporated into Microsoft Word files, sorted and labeled according to the International Conference on Harmonisation (ICH) recommendations, and formatted to the appropriate page size(s).

For categorical variables, summary tabulations of the number and percentage of patients within each category (with a category for missing data) of the parameter will be presented. For continuous variables, the number of patients, mean, median, standard deviation (SD), minimum, and maximum values will be presented.

Laboratory data (including vitamin A and RBP) collected and recorded as below the limit of detection will be set equal to the lower limit of detection for the calculation of summary statistics.

For assessments that are repeated multiple times on the study day (e.g., 10-meter walk tests, IENFD, SGNFD, etc.), the average will be calculated unless otherwise noted.

Formal statistical hypothesis testing will be performed on the primary and secondary efficacy endpoints with all tests conducted at the nominal 2-sided 0.05 level of significance. Secondary endpoints will be tested in a prespecified hierarchy (Section 3.6). Summary statistics will be presented, as well as 2-sided 95% confidence intervals on selected parameters, as described in the sections below.

All summaries will be presented by treatment arm. All data recorded on the CRF will be included in data listings.

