The estimated worldwide prevalence of FAP is 5,000 to 10,000, with the majority of cases in Portugal, Sweden, France, Japan, Brazil, and the United States.^{8,9} The most common causative mutation of FAP is TTR Val30Met (V30M), with the onset of symptoms typically occurring between 30 and 55 years of age.¹⁰ Amyloid deposition occurs largely in the peripheral nerves, starting as a nerve length-dependent sensory polyneuropathy in the feet causing numbness and pain and progressing to painful dysesthesias. Disabling motor neuropathy follows, characterized by leg weakness and eventual inability to walk. Autonomic neuropathy is another common feature of the disease, resulting in severe gastrointestinal pathology (including diarrhea or constipation and malabsorption, leading to severe malnutrition), orthostatic hypotension, and bladder dysfunction with recurring urinary tract infections.^{11,12,13,14} For several mutations, cardiac pathology also occurs due to amyloid infiltration of the sinus node, atrioventricular conduction system, and infiltration of the myocardium.^{15,16} Involvement of the conduction system can lead to sudden death due to dysrhythmias, and myocardial infiltration can lead to diastolic dysfunction and right-sided heart failure.¹⁷ The cardiomyopathy proceeds inexorably, leading to death typically within 10 years.¹⁸

There are multiple lines of evidence demonstrating that reduction of circulating TTR improves outcomes in patients with ATTR. Because the liver is the primary source of WT and mutant TTR, orthotopic liver transplantation has been used since 1990 in an attempt to treat FAP,¹⁹ and is the current standard of care in patients who are eligible for transplant (patients with minimal neuropathy symptoms and no cardiac involvement).

When liver transplantation is performed early in the course of the disease, it can stabilize and slow the course of neuropathic disease in patients with FAP due to V30M, but is less effective in patients with other TTR mutations.²⁰ However, it is less effective in patients with more advanced disease, especially those with heart involvement, due to the continued production and deposition of WT TTR in tissues with pre-existing amyloid.^{21,22,23}

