7.2.4 Intraepidermal Nerve Fiber Density and Sweat Gland Nerve Fiber Density

Quantification of nerve fibers in skin will be assessed via IENFD and SGNFD. Patients who have provided additional voluntary consent for skin biopsy will undergo tandem 3mm skin punch biopsies for IENFD and SGNFD assessment. At each time point, 1 set of biopsies will be taken from the distal lower leg, when a patient's clinical status allows, and 1 set from the distal thigh (4 biopsies total).

A repeat baseline biopsy may be performed if the initial sample is not of sufficient quality.

Details on sample collection, processing, and storage will be provided in the Study Laboratory Manual.

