4.3.3. Exploratory Efficacy Evaluations

The continuous exploratory endpoints including grip strength, SGNFD, IENFD, dermal amyloid content, EQ-5D-5L index, EQ VAS, original NIS+7 and small/large fiber function (defined in Appendix 7.2.1) will be analyzed using an MMRM model similar to those employed for the primary analysis.

The categorical exploratory endpoints PND score and FAP stage will be descriptively summarized by presenting the number and percentage of patients in each category for each visit. The number of percentage of patients with improving, no change, and worsening in PND/FAP at each visit will also be summarized.

For EQ-5D-5L, a categorical summary of the numbers and percentages of patients reporting each ordinal response within each EQ-5D domain will be presented.

Cardiac structure and function will be assessed for all patients through echocardiograms. Cardiac stress and injury will be measured using serum levels of the cardiac biomarkers NT-proBNP and troponin I. Quantification of these biomarkers will be performed at a central laboratory. Descriptive statistics will be provided for actual values, changes, and percentage changes from baseline in echocardiogram parameters, serum levels of troponin I and NT-proBNP by treatment arm.

For cardiac subpopulation (defined in Section 4.2), the change from baseline to Month 18 in LV wall thickness, LV mass, LVEF, LV longitudinal strain, NT-proBNP and troponin I will be compared between the 2 treatment arms using MMRM. The model will include baseline value

as covariate and fixed effect terms including treatment arm, visit, and treatment-by-visit interaction.

All echocardiogram and cardiac function biomarkers data will be presented in data listings.

MR neurography data will be presented in a data listing.

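### SAP 3.2 and 4.3.3 do not separate biopsy sites when averaging IENFD and SGNFD, so a leg set present at one visit but not another can shift the change score

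*SAP*

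**What the plan says.** **Sampling.** Protocol 7.2.4 calls for four punches per time point, as two tandem sets. On the first set it says: "1 set of biopsies will be taken from the distal lower leg, when a patient's clinical status allows". The second is described as "and 1 set from the distal thigh (4 biopsies total" and carries no such condition. The biopsies apply only to "Patients who have provided additional voluntary consent for skin biopsy". The schedule footnotes and the visit sections repeat the two-site scheme.

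**Averaging.** SAP 3.2 has a general rule: "For assessments that are repeated multiple times on the study day (e.g., 10-meter walk tests, IENFD, SGNFD, etc.), the average will be calculated". The sentence ends with an exception clause, "the average will be calculated unless otherwise noted". No exception for biopsy site appears in the readable text.

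**Analysis.** SAP 4.3.3 lists "The continuous exploratory endpoints including grip strength, SGNFD, IENFD, dermal amyloid content" and further measures for an MMRM like the primary one. Each biopsy measure is named once, with no site. SAP 3.4 gives no baseline by site. The partial-imputation rule in SAP 3.8.1 covers only primary and secondary endpoints, so no readable rule covers a missing leg set.

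**The concern.** Two punches side by side at one site are replicates. A leg punch and a thigh punch are not: they measure different places, and the disease need not affect both equally. Protocol 1.1.1 describes the neuropathy as "starting as a nerve length-dependent sensory polyneuropathy in the feet", which makes lower density at the leg than at the thigh plausible.

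If all same-day values are averaged, a patient with both sets at baseline and only the thigh set at Month 18 has a leg-and-thigh mean compared with a thigh-only value. The difference mixes biological change with a change of site. The MMRM cannot repair this, because the Month 18 value counts as observed and its missing-at-random handling never applies.

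Only the leg set depends on clinical status, so its absence may be informative. The SAP recognises this kind of problem elsewhere: in 5.7 it sets walk speed to 0 for patients who cannot walk, on the ground that such missingness is informative.

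**Working it through.** The plan gives no density, sample size or power for IENFD or SGNFD, so there is no figure to reproduce. The check is direct arithmetic.

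**From the documents.** Two sites with two punches each; the leg set conditional; one value per visit if the averaging rule is read literally.

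**Assumed, not in the documents.** Thigh-to-leg density ratio r from 0.8 to 3; share of patients lacking the leg set at only one of the two visits compared, 5% to 30%.

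**Per patient, no true change.** Let L be leg density and T = r × L thigh density.
- Both sets taken: mean = (2L + 2T)/4 = (L + T)/2.
- Thigh set only: mean = T.
- Leg set lost after baseline: T − (L + T)/2 = (T − L)/2, which is (r − 1)/(r + 1) of the baseline mean.
- Leg set missing only at baseline: (L + T)/2 − T = −(T − L)/2, which is −(r − 1)/(2r) of the thigh-only baseline.
- Leg set missing at both visits: T − T = 0.

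The last column below takes a true 20% loss at both sites with the leg set lost at follow-up: 0.8T/[(L + T)/2] − 1.

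| r | Lost after baseline | Missing only at baseline | True −20% appears as |
|---|---|---|---|
| 0.8 | −11.1% | +12.5% | −28.9% |
| 1.0 | 0% | 0% | −20.0% |
| 1.25 | +11.1% | −10.0% | −11.1% |
| 1.5 | +20.0% | −16.7% | −4.0% |
| 2.0 | +33.3% | −25.0% | +6.7% |
| 3.0 | +50.0% | −33.3% | +20.0% |

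**Arm mean.** Shift = share affected × per-patient shift. At r = 1.5, if 5%, 10%, 20% or 30% of an arm loses the leg set after baseline, the arm mean moves by 0.05 × 20 = 1.0, 0.10 × 20 = 2.0, 0.20 × 20 = 4.0 or 0.30 × 20 = 6.0 percentage points.

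**Between arms.** With the same density gap in both arms, bias in patisiran minus placebo = (patisiran share − placebo share) × (T − L)/2, counting leg sets lost after baseline. With assumed gaps in fibers/mm:
- 5-point difference in shares, gap 3: 0.05 × 3/2 = 0.075.
- 20-point difference, gap 6: 0.20 × 6/2 = 0.60.

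The sign follows the difference in shares. Against an assumed true benefit of 1.0, a 10-point difference with gap 6 gives 0.10 × 6/2 = 0.30. The estimate is then 0.70 if placebo loses more leg sets and 1.30 if patisiran does. Equal shares give no bias between arms.

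**After the fix.** If change is taken within a site, T is compared with T and L with L, and the artefact is 0 for every r.

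**The case against.** The strongest reply is that the SAP does not prescribe cross-site pooling. Its rule covers repeated assessments, and one of its examples, the walk test, is the same test done again. The tandem punches at one site fit that description well, whereas leg and thigh are different measurements. On that reading no artefact arises. This stands as a possible reading, but the text does not select it. All four values are same-day IENFD or SGNFD values, SAP 4.3.3 has one endpoint per measure, and nothing says how two site means would become one endpoint. A programmer following the words could reasonably pool.

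Parts of the SAP appendices are redacted, so a site rule there cannot be excluded. Neither 3.2 nor 4.3.3 points to one.

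A reader might infer that the plan builds in a false improvement, or a bias against patisiran because worsening placebo patients lose the leg set. The documents do not support either. They give no densities and no leg-missing rates by arm, do not define the clinical-status condition, and do not say that worsening leads to omission. A set missing only at baseline acts in the opposite direction. Nor do they state that two sites were chosen to compare distal with proximal effects, so pooling cannot be faulted for defeating a declared aim.

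The reach is also narrow: SAP 3.2 confines formal testing to primary and secondary endpoints, and these are neither.

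**Conclusion.** The point holds in a limited form. Read literally, the averaging rule and the single-endpoint model yield one cross-site value per visit. A change in the sites sampled then moves the raw change score by (thigh − leg)/2. Over assumed ratios of 1.25 to 3, the per-patient artefact with no true change is +11.1% to +50.0% when the leg set is lost after baseline, and −10.0% to −33.3% when it is missing only at baseline. It is zero when sampling is the same at both visits or the two densities are equal, and it reverses if thigh density is the lower.

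The rise or fall rests on three conditions: pooling across sites, unequal densities, and a leg set present at one visit but not the other. Protocol 1.1.1 makes higher thigh density plausible but does not quantify it. Between-arm bias is proportional to the difference in missing-leg rates; its size and direction cannot be determined from the documents. The primary endpoint, the testing hierarchy and type I error are untouched. The correction is worth making because it is nearly free and removes the artefact whatever the true densities.

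**What to change.** In SAP 3.2, state that only the tandem punches within a site are averaged. In SAP 4.3.3, derive and model IENFD, SGNFD and dermal amyloid content (from the same specimens, per SAP 1.2.7.1) separately for distal leg and distal thigh, each as change from that site's own baseline. A missing leg set is then missing leg data and nothing else. If a combined value is kept, compute its change only from sites sampled at both visits being compared.

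Tabulating by arm and visit how many consenting patients had each set would show whether leg-set loss differs between arms. The wording should be settled before unblinding, so that the choice is not made with results in view.

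The cost is a few lines of text and one extra exploratory model per measure. The leg model may rest on fewer patients than the thigh model. No new biopsies are needed, since the protocol already takes the sets by site.
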